5.5 Diet/Activity/Other Considerations

5.5.1 Diet

Subjects should maintain a normal diet unless modifications are required to manage an AE such as diarrhea, nausea or vomiting.

5.5.2 Contraception

Pembrolizumab or IL-2 may have adverse effects on a fetus in utero. Furthermore, it is not known if pembrolizumab or IL-2 have transient adverse effects on the composition of sperm.

- Non-pregnant, non-breast-feeding women of childbearing potential (WOCBP) may be enrolled if they are abstinent from penile-vaginal intercourse or if they are willing to use 2 methods of birth control (see section 13.5) for the duration of the study period up to 140 days after the last dose of pembrolizumab.
- Male participants with female partners of childbearing potential are eligible if they are abstinent from penile-vaginal intercourse or they and their partner(s) agree to use of 2 methods of birth control (see section 13.5) for the duration of the study period up to 200 days after the last dose of pembrolizumab.

5.5.3 Use in Pregnancy

If a subject inadvertently becomes pregnant while on treatment with pembrolizumab, the subject will immediately be removed from the study. The site will contact the subject at least monthly and document the subject's status until the pregnancy has been completed or terminated. The outcome of the pregnancy will be reported to the Principal Investigator and to Merck without delay and within 24 hours if the outcome is a serious adverse experience (e.g., death, abortion, congenital anomaly, or other disabling or life-threatening complication to the mother or newborn). The study investigator will make every effort to obtain permission to follow the outcome of the pregnancy and report the condition of the fetus or newborn to the Sponsor. If a male subject impregnates his female partner the study personnel at the site must be informed immediately and the pregnancy reported to the Principal Investigator and to Merck and followed as described above and in [Section 7.3.2](#).

5.5.4 Use in Nursing Women

It is unknown whether pembrolizumab is excreted in human milk. Since many drugs are excreted in human milk, and because of the potential for serious adverse reactions in the nursing infant, subjects who are breast-feeding are not eligible for enrollment.

5.6 Subject Withdrawal/Discontinuation Criteria

Subjects may withdraw consent at any time for any reason or be dropped from the trial at the discretion of the investigator should any untoward effect occur. In addition, a subject may be withdrawn by the investigator or the Principal Investigator if enrollment into the trial is inappropriate, the trial plan is violated, or for administrative and/or other safety reasons.

Specific details regarding discontinuation or withdrawal are provided in [Section 7.2.4](#) – Other Procedures.

A subject must be discontinued from the trial for any of the following reasons:

- The subject withdraws consent.
- Confirmed radiographic disease progression

Note: A subject may be granted an exception to continue on treatment with confirmed radiographic progression if clinically stable or clinically improved, please see [Section 5.7](#)

- Unacceptable adverse experiences as described in [Section 5.2](#).
- Intercurrent illness that prevents further administration of treatment
- Investigator's or Principal Investigator's decision to withdraw the subject
- The subject has a confirmed positive serum pregnancy test
- Noncompliance with trial treatment or procedure requirements
- The subject is lost to follow-up
- Administrative reasons

The End of Treatment and Follow-Up visit procedures are listed in Section 6 (Protocol Flow Chart) and [Section 7.2.5](#) (Visit Requirements). After the end of treatment, each subject will be followed for 30 days for adverse event monitoring (serious adverse events will be collected for 90 days after the end of treatment as described in [Section 7.3.3.1](#)). Subjects who discontinue for reasons other than progressive disease will have post-treatment Surveillance Follow-Up for disease status until disease progression, initiating a non-study cancer treatment, withdrawing consent or becoming lost to follow-up. After documented disease progression each subject will be followed by telephone for Survival Follow-Up until death, withdrawal of consent, or the end of the study, whichever occurs first.

5.7 Treatment After Initial Evidence of Radiologic Disease Progression

Immunotherapeutic agents may produce antitumor effects by potentiating endogenous cancer-specific immune responses which may be functionally anergic. The response patterns seen with such an approach may extend beyond the typical time course of responses seen with cytotoxic agents, and can manifest a clinical response after an initial increase in tumor burden or even the appearance of new lesions. In subjects who have initial evidence of radiological PD following a first course of treatment, it is at the discretion of the treating physician whether to continue a subject on study treatment for a second treatment course. This decision should be based on the clinical judgment of the subject's overall clinical condition, including performance status, clinical symptoms, laboratory data, and tolerance for study treatments.

Subjects recommended to receive a second treatment course after PD should meet the following criteria:

- Absence of signs and symptoms indicating disease progression
- Absence of progressive tumor at critical anatomical sites (e.g., cord compression) requiring urgent alternative medical intervention
- Absence of rapid progression of disease
- No decline in ECOG performance status

This allowance takes into account the observation that some subjects can have a transient tumor flare in the first few months after the start of immunotherapy, but with subsequent disease response.

5.8 Clinical Criteria for Early Trial Termination

Early trial termination will be the result of the criteria specified below:

1. Quality or quantity of data recording is inaccurate or incomplete
2. Poor adherence to protocol and regulatory requirements
3. Incidence or severity of adverse drug reaction in this or other studies indicates a potential health hazard to subjects
4. Plans to modify or discontinue the development of the study drug

In the event of Merck decision to no longer supply study drug, ample notification will be provided so that appropriate adjustments to subject treatment can be made.

6.0 TRIAL FLOW CHART

6.1 Study Flow Chart

Trial Period:		Study Screening	Treatment Courses ¹												Post-Treatment			
Treatment Cycle/Title:			1			2			3			4			Safety Follow-Up	Surveillance Follow-Up ²	Survival Follow-Up ³	
Treatment Week			1	2	3	4	5	6	7	8	9	10	11	12				
Scheduling Window (Days):	-28 to -1		±2	±2	±2	±2	±2	±2	±2			±2		±7	30 (±7) days post EOT ⁴	Every 12 (±1) week post EOT	Every 12 (±1) week	
Administrative Procedures																		
Informed Consent																		
Inclusion/Exclusion Criteria	X																	
Demographics and Medical History	X																	
Prior and Concomitant Medication Review	X																	
Pembrolizumab Administration		X			X			X				X						
SQ IL-2 Administration		X ⁵	X ⁵	X ⁵	X ⁵	X ⁵	X ⁵											
IV IL-2 Administration		X ⁶			X ⁶													
Post-study anticancer therapy status															X	X	X	
Survival Status															X	X	X	
Clinical Procedures / Assessments																		
Review Adverse Events		X	X ^{7,8}	X ⁷	X	X ^{7,8}	X ⁷	X				X			X			
Physical Examination	X	X	X ^{7,8}	X ⁷	X	X ^{7,8}	X ⁷	X				X			X	X		
Vital Signs ⁹ and Weight	X	X	X ^{7,8}	X ⁷	X	X ^{7,8}	X ⁷	X				X			X	X		
ECOG Performance Status	X	X	X ^{7,8}	X ⁷	X	X ^{7,8}	X ⁷	X				X			X	X		
Laboratory Procedures/Assessments: analysis performed by local laboratory																		
Pregnancy Test – Urine or Serum β -HCG ¹⁰	X	X ¹⁰													X			

Trial Period:	Study Screening	Treatment Courses ¹												Post-Treatment		
		1			2			3			4			Safety Follow-Up	Surveillance Follow-Up ²	Survival Follow-Up ³
Treatment Cycle/Title:		1	2	3	4	5	6	7	8	9	10	11	12			
Treatment Week		1	2	3	4	5	6	7	8	9	10	11	12			
Scheduling Window (Days):	-28 to -1	±2	±2	±2	±2	±2	±2	±2		±2	±2	±7		30 (±7) days post EOT ⁴	Every 12 (±1) week post EOT	Every 12 (±1) week
HIV, Hepatitis-B and -C ¹¹	X															
PT/INR and aPTT	X ⁶															
CBC with Differential	X	X ¹²	X ^{7,8}	X ⁷	X	X ^{7,8}	X ⁷	X			X			X	X	
Basic Metabolic Panel	X	X ¹²	X ^{7,8}	X ⁷	X	X ^{7,8}	X ⁷	X			X			X	X	
Hepatic Function Panel w/LD	X	X ¹²	X ^{7,8}	X ⁷	X	X ^{7,8}	X ⁷	X			X			X	X	
FT4 and TSH	X	X ¹²			X			X			X			X	X	
Amylase and Lipase	X	X ¹²			X			X			X			X		
Troponin-I	X	X			X			X ¹³			X ¹³					
Urinalysis	X															
EKG	X															
Cardiac Function Testing ¹⁴	X															
Pulmonary Function Testing ¹⁵	X															
Cardiac Stress Testing ¹⁶	X															
Efficacy Measurements																
Tumor Imaging ¹⁷	X											X		X		
Archival Tissue Collection / Tumor Biopsy / Correlative Studies																
Archival or Newly Obtained Tissue Collection		X ¹⁸														
Peripheral blood for T cell subset quantitation by flow cytometry		X ¹⁸						X					X		X	

Trial Period:	Study Screening	Treatment Courses ¹												Post-Treatment		
		1			2			3			4			Safety Follow-Up	Surveillance Follow-Up ²	Survival Follow-Up ³
Treatment Cycle/Title:		1	2	3	4	5	6	7	8	9	10	11	12			
Treatment Week		1	2	3	4	5	6	7	8	9	10	11	12			
Scheduling Window (Days):		-28 to -1	± 2	± 7	30 (± 7) days post EOT ⁴	Every 12 (± 1) week post EOT	Every 12 (± 1) week									
Peripheral blood for future correlative studies		X ¹⁸												X		X

¹Maximum duration of therapy is 3 courses.

²Post-treatment surveillance for patients with SD, PR, or CR.

³After PD, start of new cancer treatment, or completion of 1 year Surveillance Follow-Up

⁴EOT = end of treatment

⁵Dose Level 1 patients only. For each cycle day 1, administer IL-2 after pembrolizumab. Observe patients \geq 1 hour after the first pembrolizumab dose (day 1, cycle1) before administering the first SQ IL-2 dose.

⁶Dose Level 2 and 3 patients only. Patients will admit to begin IV IL-2 treatment on cycle day 2, (or next available ICU admission day).

⁷Evaluations for Dose Level 1 patients week 2,3,5,6 are only required during Course 1

⁸Evaluations for Dose Level 2 and 3 patients on week 2 and 5 follow hospital discharge for IL-2 cycles 1 and 2 respectively.

⁹Vital signs to include temperature, heart rate, respiratory rate, blood pressure, and pulse oximetry.

¹⁰A negative pregnancy test must be documented $<$ 72 hrs before each day 1 pembrolizumab dose for the start of each treatment course and at EOT. Pregnancy testing should be repeated whenever an expected menstrual cycle is missed or when pregnancy is otherwise suspected.

¹¹Screening serologies within 28 days of day 1

¹²Don't repeat labs cycle 1/day 1 if screening labs are $<$ 14 days old.

¹³Troponin-I testing prior to pembrolizumab cycle 3 and 4 required for course 1 only

¹⁴LVEF \geq 50% measured by MUGA scan, echo, or stress test study with myocardial perfusion imaging. A cardiac study documenting LVEF \geq 50% (MUGA, echo, or stress testing) obtained prior to study enrollment and within 6 months of study day 1 is acceptable screening and does not need to be repeated.

¹⁵Screening studies for Dose Level 2 and 3 patients only. PFT testing completed prior to study enrollment and within 6 months of study day 1 is acceptable screening and does not need to be repeated

¹⁶Myocardial ischemia screening by normal/negative cardiac stress testing with myocardial perfusion imaging. **OR** cardiac catheterization with non-significant angiogram findings reviewed by a Cardiology consultant. Prior normal cardiac stress testing or negative cardiac angiogram findings obtained prior to study enrollment and within 6 months of study day 1 is acceptable screening and does not need to be repeated.

¹⁷Baseline imaging to include brain (MRI preferred; contrast CT acceptable) and chest, abdomen, and pelvis by CT or MRI. Bone scan required for patients with known bone involvement on CT or MRI. Restaging assessments to include chest, abdomen, pelvis body parts with brain imaging or bone scan required only for patients with tumor findings on

these studies at baseline. Body imaging studies obtained prior to study enrollment and \leq 6 weeks from the start of study treatment are acceptable as baseline studies and do not need to be repeated.

¹⁸Collect blood samples for all eligible patients after screening is completed and before C1D1 treatment. Blood samples can be collected before C1D1 or on C1D1 before treatment is given. Confirmation of available archival tissue samples prior to C1D1 treatment.

7.0 TRIAL PROCEDURES

7.1 Subject Registration

All subjects will be registered and entered into the University of Washington protocol accrual and patient tracking system. Patients must be registered prior to starting protocol therapy.

Documented informed consent, HIPAA authorization, and verification of subject eligibility must be completed prior to subject registration and assignment of a unique study number.

If a patient is consented to the trial but is not registered or is withdrawn prior to initiation of protocol treatment, the reason for screen failure and/or withdrawal will be documented.

However, no clinical trial data will be collected beyond the basic demographic data contained on the eligibility checklist. The site (University of Washington) will use a registration log with entries for each patient registered.

7.2 Trial Procedures

The Trial Flow Chart - [Section 6.0](#) summarizes the trial procedures to be performed at each visit. Individual trial procedures are described in detail below. It may be necessary to perform these procedures at unscheduled time points if deemed clinically necessary by the investigator.

Furthermore, additional evaluations/testing may be deemed necessary by the investigator and/or Merck for reasons related to subject safety.

7.2.1 Administrative Procedures

7.2.1.1 General Informed Consent

Consent must be documented by the subject's dated signature on a consent form along with the dated signature of the person conducting the consent discussion. The investigator will obtain documented consent from each potential subject prior to conducting any study procedures in the clinical trial.

A copy of the signed and dated consent form should be given to the subject before participation in the trial.

The initial informed consent form, any subsequent revised written informed consent form and any written information provided to the subject must receive the IRB/ERC's approval/favorable opinion in advance of use. The subject should be informed in a timely manner if new information becomes available that may be relevant to the subject's willingness to continue participation in the trial. The communication of this information will be provided and documented via a revised consent form or addendum to the original consent form that captures the subject's dated signature.

The informed consent will adhere to IRB/ERC requirements, applicable laws and regulations and Sponsor requirements.

7.2.1.2 Inclusion/Exclusion Criteria

All inclusion and exclusion criteria will be reviewed by the investigator or qualified designee to ensure that the subject qualifies for the trial.

7.2.1.3 Medical History

A medical history will be obtained by the investigator or qualified designee. Medical history will include all active conditions, and any condition diagnosed within the prior 10 years that are considered to be clinically significant by an investigator. Details regarding the disease for which the subject has enrolled in this study will be recorded separately and not listed as medical history.

7.2.1.4 Prior and Concomitant Medications Review

7.2.1.4.1 Prior Medications

The investigator or qualified designee will review prior medication use, including any protocol-specified washout requirement, and record prior medication taken by the subject immediately before starting trial therapies. Treatment for the disease for which the subject has enrolled in this study will be recorded separately and not listed as a prior medication.

7.2.1.4.2 Concomitant Medications

The investigator or qualified designee will record medication, if any, taken by the subject during the trial. All medications related to reportable SAEs and ECIs should be recorded as defined in [Section 7.3](#).

7.2.1.5 Disease Details and Treatments

7.2.1.5.1 Disease Details

The investigator or qualified designee will obtain prior and current details regarding disease status.

7.2.1.5.2 Prior Treatment Details

The investigator or qualified designee will review all prior cancer treatments including systemic treatments, radiation and surgeries.

7.2.1.5.3 Subsequent Anti-Cancer Therapy Status

The investigator or qualified designee will review all new anti-neoplastic therapy initiated after the last dose of trial treatment. If a subject initiates a new anti-cancer therapy within 30 days after the last dose of trial treatment, the 30 day Safety Follow-Up visit must occur before the first dose of the new therapy. Once new anti-cancer therapy has been initiated the subject will move into Survival Follow-Up.

7.2.2 Clinical Procedures/Assessments

7.2.2.1 Adverse Event (AE) Monitoring

The investigator or qualified designee will assess each subject to evaluate for potential new or worsening AEs as specified in the Trial Flow Chart and more frequently if clinically indicated. Adverse experiences will be graded and recorded throughout the study and during the Follow-Up period according to the NCI CTCAE v5.0 (see [Section 13.2](#)). Toxicities will be characterized in terms regarding seriousness, causality, toxicity grading, and action taken with regard to trial treatment.

For subjects receiving treatment with pembrolizumab all AEs of unknown etiology associated with pembrolizumab exposure should be evaluated to determine if it is possibly an event of clinical interest (ECI) of a potentially immunologic etiology (termed immune-related adverse events, or irAEs); (see the separate ECI guidance document regarding the identification, evaluation and management of potential irAEs).

Please refer to [section 7.3](#) for detailed information regarding the assessment and recording of AEs.

7.2.2.2 Physical Exam

The investigator or qualified designee will perform a complete physical exam during the screening period. Clinically significant abnormal findings should be recorded as medical history. A complete physical exam should also be performed at monitoring visits performed during the Treatment and Follow-Up phases of the study.

7.2.2.3 Vital Signs

Vital signs will be collected at screening, prior to the administration of each dose of trial treatment and at treatment discontinuation as specified in the Trial Flow Chart ([Section 6.0](#)). Vital signs should include temperature, pulse, respiratory rate, weight, blood pressure and pulse oximetry.

7.2.2.4 Eastern Cooperative Oncology Group (ECOG) Performance Scale

The investigator or qualified designee will assess ECOG status (see [Section 13.1](#)) at screening, prior to the administration of each dose of trial treatment and discontinuation of trial treatment as specified in the Trial Flow Chart.

7.2.2.5 Tumor Imaging and Assessment of Disease

Tumor imaging by CT or MRI scans will be obtained at screening, at the end of each treatment course, and every 12 weeks following completion of therapy for patients who remain in Surveillance Follow-Up as specified in the Trial Flow Chart ([Section 6.0](#)). Disease status will be assessed versus baseline imaging for response category by RECIST 1.1 criteria (see Section 13.3).

7.2.2.6 Tumor Tissue Collection and Correlative Studies Blood Sampling

Blood and tissue collections for correlative studies will be obtained as specified in the Trial Flow Chart ([Section 6.0](#)).

7.2.3 Laboratory Procedures/Assessments

Details regarding specific laboratory procedures/assessments to be performed in this trial are provided below. Laboratory Safety Evaluations (Hematology, Chemistry and Urinalysis)

Laboratory tests for hematology, chemistry, urinalysis, and others are specified in Table 6.

Table 6 Laboratory Tests

Hematology	Chemistry	Urinalysis	Other
WBC (total and differential)	Lactate dehydrogenase (LDH)	Specific gravity	Serum β -human chorionic gonadotropin†
Hemoglobin	Amylase	pH	(β -hCG)†
Hematocrit	Lipase	Protein	
MCV	Aspartate aminotransferase (AST)	Glucose	PT (INR)
Platelet count	Alanine aminotransferase (ALT)	Ketones	aPTT
	Alkaline phosphatase	Bilirubin, Qual	Free tyroxine (T4)
	Total Bilirubin	Occult Blood	Thyroid stimulating hormone (TSH)
	Direct Bilirubin	Nitrite	Troponin-I
	Total protein	Leukocyte Esterase	
	Albumin	Urobilinogen	Blood for correlative studies
		Microscopic exam (If abnormal)	
	Sodium	results are noted	
	Potassium		
	Chloride	Urine pregnancy test †	
	Carbon Dioxide		
	Glucose		
	Blood Urea Nitrogen		
	Creatinine		
	Calcium		

† Perform on women of childbearing potential only. If urine pregnancy results cannot be confirmed as negative, a serum pregnancy test will be required.

Laboratory tests for screening or entry into the Second Course Phase should be performed within 14 days prior to the first dose of treatment. After pembrolizumab Cycle 1, pre-dose laboratory procedures can be conducted up to 72 hours prior to dosing. Results must be reviewed by the investigator or qualified designee and found to be acceptable prior to each dose of trial treatment.

7.2.4 Other Procedures

7.2.4.1 Discontinuation

When a subject discontinues study treatment prior to trial completion, all applicable activities scheduled for the final trial visit should be performed at the time of discontinuation. Any adverse events which are present at the time of discontinuation should be followed in accordance with the safety requirements outlined in [Section 7.3](#) - Assessing and Recording Adverse Events. Subjects who attain a CR should return to the site for a Safety Follow-Up Visit (described in [Section 7.2.5.2](#)) and then proceed to the Surveillance Follow-Up Period of the study (described in [Section 7.2.5.2.1](#)).

7.2.5 Visit Requirements

Visit requirements are outlined in [Section 6.0](#) - Trial Flow Chart. Specific procedure-related details are provided above in [Section 7.2](#) - Trial Procedures.

7.2.5.1 Safety Follow-Up Visit

The mandatory Safety Follow-Up Visit should be conducted 30 (± 7) days after the last dose of trial treatment or before the initiation of a new anti-cancer treatment, whichever comes first. All treatment-related AEs that occur prior to the Safety Follow-Up Visit should be recorded. Subjects with an AE of Grade > 1 will be followed until the resolution of the AE to Grade 0-1 or until the beginning of a new anti-neoplastic therapy, whichever occurs first. SAEs that occur within 90 days of the end of treatment should also be followed and recorded.

7.2.5.2 Surveillance Follow-Up Visits

Subjects who complete or discontinue trial treatment with a disease status of CR, PR or SD will move into the Surveillance Follow-Up Phase and should be assessed every 12 weeks (84 ± 7 days) by radiologic imaging to monitor disease status. Every effort should be made to collect information regarding disease status until the start of new anti-neoplastic therapy, disease progression, death, or end of the study. Information regarding post-study anti-neoplastic treatment will be collected if new treatment is initiated.

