DSMC	Data Safety Monitoring Committee
DSMP	Data and Safety Monitoring Plan
EC	Ethics committee
ECG/EKG	Electrocardiogram
ECI	Event of clinical interest
ECOG	Eastern Cooperative Oncology Group
EOT	End of treatment
ERC	Ethics Review Committee
EU	European Union
FDA	Food and Drug Administration
FDAAA	Food and Drug Administration Amendments Act
FDAMA	Food and Drug Administration Modernization Act
FEV1	Forced expiratory volume in 1 second
FFPE	Formalin fixed, paraffin embedded
Fred Hutch	Fred Hutchinson Cancer Center
FT4	Free T4
FVC	Forced vital capacity
GI	Gastrointestinal specialist (Gastroenterology)
GFR	Glomerular filtration rate
Hct	Hematocrit
HCV	Hepatitis C virus
HD	High-Dose
HDIL-2	High-Dose Interleukin-2
HIF	Hypoxia-inducible factor
HIPAA	Health Insurance Portability and Accountability Act
HIV	Human Immunodeficiency Virus
hr	hour
HR	Hazard ratio
HSV	Herpes simplex virus
IB	Investigator's brochure
ICU	Intensive care unit
IEC	Independent ethics committee
IFN- α	interferon-alfa
IFN- γ	Interferon-gamma
Ig	Immunoglobulin
IHC	Immunohistochemistry
IL-2	Interleukin-2

IND	Investigational New Drug
INR	International normalized ratio
irAEs	immune-related Adverse Events
IRB	Institutional Review Board
IV	Intravenous
K	potassium
kg	kilogram
L	Liter
LD/LDH	Lactate dehydrogenase
LFT	Liver function tests
LVEF	Left ventricular ejection fraction
MAP	Mean arterial pressure
mAb	monoclonal antibody
mcg	microgram
mcL	microliter
MCV	Mean corpuscular volume
MD	Medical doctor
mg	milligram
Mg	Magnesium
min	minute
mL	milliliter
mmol	millimole
MRI	Magnetic resonance imaging
MTD	Maximum tolerated dose
mTOR	mammalian Target of Rapamycin
MUGA	Multiple-Gated Acquisition Scan
N	Number
NCI	National Cancer Institute
NK	Natural killer cell
NSAID	Nonsteroidal anti-inflammatory drug
NSCLC	Non-small cell lung cancer
ORR	Objective response rate
OTC	Over-the-counter
PATS	Protocol Accrual Tracking System
PD	Progressive disease
PD1	Programmed Cell Death 1
PD-L1	Programmed Cell Death 1 - Ligand 1

PD-L2	Programmed Cell Death 1 - Ligand 2
PFS	Progression-free survival
pH	potential of Hydrogen
PhD	Doctor of Philosophy
Phos	Phosphate
PICC	Peripherally inserted central catheter
PK	Pharmacokinetic
Plts	Platelets
PMDA	Pharmaceutical and Medical Devices Agency
PO	Per os (by mouth)
PR	Partial response
PT	Protome
Q1h	Every hour
Q2W	Every 2 weeks
Q3W	Every 3 weeks
Q4h	Every 4 hours
RCC	Renal cell carcinoma
RECIST	Response Evaluation Criteria in Solid Tumors
RN	Registered nurse
R/O	Rule out
RR	Risk ratio

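### Surveillance imaging has conflicting entry rules and runs from an undated end of treatment, so a patient who stops mid-course has no clearly required course-end scan and may be scanned about 3 to 6 weeks late

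*Combined protocol and SAP*

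**What the plan says.** **Entry to Surveillance.** Section 7.2.5.2 goes by disease status: "Subjects who complete or discontinue trial treatment with a disease status of CR, PR or SD will move into the Surveillance Follow-Up Phase". Footnote 2 of the flow chart (Section 6.1) also limits Surveillance to patients with SD, PR or CR. Section 5.6 goes by reason for stopping and asks for no RECIST category: "Subjects who discontinue for reasons other than progressive disease will have post-treatment Surveillance Follow-Up for disease status until disease progression", with new treatment, withdrawal of consent and loss to follow-up as the other end points.

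**Timing.** Section 7.2.2.5 places scans at screening, then "at the end of each treatment course, and every 12 weeks following completion of therapy for patients who remain in Surveillance Follow-Up". The flow chart heads the Surveillance column "Every 12 (±1) week post EOT", and Section 7.2.5.2 says these patients "should be assessed every 12 weeks (84 ± 7 days) by radiologic imaging to monitor disease status". EOT is spelled out as end of treatment, but no rule says which date that is.

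**At discontinuation.** Section 7.2.4.1 says that "all applicable activities scheduled for the final trial visit should be performed at the time of discontinuation". It does not identify that visit or mention imaging.

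**Analysis.** Section 9.1 measures PFS from registration and censors patients who are alive without progression at their last disease assessment. Section 4.2.4.2 reports ORR, DCR and PFS by cohort and for all treated patients, and compares them with historical data. Under Section 7.2.1.5.3, starting a new anti-cancer therapy moves the patient to Survival Follow-Up, which is by telephone (Section 7.2.5.2.1).

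**The concern.** Take a patient who stops for toxicity in week 4 of course 1. No post-baseline scan has been done, so the patient has no CR, PR or SD. Section 5.6 puts this patient in Surveillance; Section 7.2.5.2 and footnote 2 do not. Two staff members reading different sections could image the same patient differently.

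If the patient does enter, the scan clock restarts at EOT. The course-end scan is tied to a course that was not finished, and no sentence says it is still due. PFS keeps its origin at registration, so the date on which progression can be seen depends on when treatment stopped.

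If new therapy starts before any scan, imaging ends and the last disease assessment is the baseline one. Footnote 17 allows body imaging from up to 6 weeks before treatment, so that date may even precede registration. Section 9.1 has no rule for a patient without a post-baseline scan.

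Toxicity-driven discontinuation feeds the DLT definition (Section 5.2.1.3), so the patients affected include those a phase I trial most needs to describe. With 3 to 6 patients in an escalation cohort, one of them is a large share of the data.

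**Working it through.** The plan gives no figure for scan delay, so there is none to reproduce.

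**Inputs.** Four pembrolizumab doses every 3 weeks fall on days 1, 22, 43 and 64 of a course (Section 2.1). A course is 12 weeks, or 84 days. The Surveillance interval is 84 ± 7 days (Section 7.2.5.2).

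**Assumption.** EOT is the last pembrolizumab dose. The safety visit gives some support: the flow chart times it from EOT, and Section 7.2.5.1 times the same visit from the last dose.

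**Course 1.** First Surveillance scan = EOT day + 84; delay = that day − 84.

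| Last dose | EOT day | First scan (±7 days) | Delay |
|---|---|---|---|
| 1 | 1 | 85 | 1 day (0.1 wk) |
| 2 | 22 | 106 | 22 days (3.1 wk) |
| 3 | 43 | 127 | 43 days (6.1 wk) |
| 4 | 64 | 148 | 64 days (9.1 wk), only if the course-end scan is not done |

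**Course 2, starting on day 85, previous scan on day 84.** The doses fall on days 85, 106, 127 and 148.
- Stop after dose 2: scan on day 106 + 84 = 190; gap 190 − 84 = 106 days (15.1 weeks).
- Stop after dose 3: scan on day 127 + 84 = 211; gap 127 days (18.1 weeks).
- Dose 4, with the same proviso as above: scan on day 148 + 84 = 232; gap 148 days (21.1 weeks).

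The gap for a patient who continues is 84 days (12 weeks).

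**Effect on recorded PFS.** Assume exponential PFS with a median of 4 to 15 months (the documents give none for this regimen) and progression dated at the next scan. With S(t) the probability of being progression-free at day t, and first scan on day f followed by scans every 84 days, mean recorded PFS in days = f + 84 × S(f) / [1 − S(84)].

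At a 6-month median, S(84) = 0.727, S(106) = 0.669 and S(127) = 0.618. The means are 44.0 weeks (f = 84), 44.5 weeks (f = 106) and 45.3 weeks (f = 127).

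Across medians of 4 to 15 months, the rise in a stopper's mean is:
- stop after dose 2: 0.2 to 0.8 weeks
- stop after dose 3: 0.6 to 1.9 weeks
- day-64 ceiling: 1.0 to 3.2 weeks

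The recorded median can move either way because of the scan grid. At a 6-month true median, simulation gives 36.0 weeks for f = 84 but 27.1 weeks for f = 106.

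**Effect on DCR.** The probability of being progression-free at the first scan falls with delay: 0.727 at day 84, 0.618 at day 127 and 0.570 at day 148 (6-month median). If 1 of 3 patients is unscanned and 65% of the others have control (assumed), DCR is 0.65 × 2/3 = 0.43 over all treated patients and 0.65 over scanned patients only.

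**The case against.** The strongest reply is that the plan already catches these patients. Section 5.6 sends them to Surveillance, Section 7.2.4.1 calls for final-visit activities when they stop, and Section 7.2.5.2 asks for every effort to follow disease status. This makes a total absence of scans less likely. It does not remove the conflict with Section 7.2.5.2 and footnote 2. A scan on the day of stopping, if Section 7.2.4.1 means one, would still leave later scans timed from EOT.

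Three stronger readings are tempting, and the documents do not support them.

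- **A delay of 9 weeks, or a 21-week gap, as the usual size.** This needs EOT on day 64. If dose 4 was given, the course's dosing is complete and Section 7.2.2.5 still calls for a course-end scan. Otherwise EOT must be dated to a decision to stop on day 64. It is a ceiling. A shift of about two months in median PFS should not be inferred from it either, since the median can move in either direction.
- **Disease control biased upward.** A later first scan lowers it, and so does an unscanned patient kept among all treated patients. It rises only if unscanned patients leave the denominator, which the plan does not say.
- **A demonstrably larger effect in the higher-dose cohorts.** Section 5.2.1.3 links bolus IL-2, above all at Dose Level 3, with severe acute toxicity, so more stopping there is plausible. No stopping rate is given. IL-2 doses can be withheld or reduced, or a modification applied to one drug, without ending study treatment. If EOT falls at the end of an IV IL-2 cycle (day 6 or 27), the first scan is on day 90 or 111, a delay of about 1 or 4 weeks.

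**Conclusion.** The point stands as a conflict between sections and a gap in scan timing. Entry to Surveillance is defined in two incompatible ways, and a patient who stops mid-course has no clearly required course-end scan. With EOT taken as the last pembrolizumab dose, the first scan is about 0, 3 or 6 weeks late after dose 1, 2 or 3 of course 1, and the gap between scans is about 15 or 18 weeks after dose 2 or 3 of course 2. A different dating of EOT would change these figures.

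The rise in mean recorded PFS is modest: under 2 weeks per affected patient for stops after dose 2 or 3, under the exponential assumption. The effect of a patient censored at or near baseline cannot be sized from the documents. The consequence is limited to secondary, descriptive endpoints in 12 to 15 patients; the primary safety analysis does not depend on it. The change is worth making because it is cheap.

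**What to change.** 1. Reconcile Section 5.6, Section 7.2.5.2 and flow-chart footnote 2. Every patient who ends treatment without documented progression should enter Surveillance, including those with no post-baseline scan.
2. In Sections 7.2.2.5 and 7.2.5.2 and the flow chart, state that a patient who stops mid-course is still imaged on the date the current course's end-of-course scan was due (±7 days). Imaging then continues every 12 weeks from that date until progression, new anti-cancer therapy or the existing follow-up limit.
3. Leave end-of-course scans as they are for patients still on treatment. A fixed calendar from day 1 for everyone would separate scans from courses that start late: Section 2.1 requires response assessment before the next course, and Section 5.2.1.4 allows interruptions.

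The nominal delay for a patient who stops in course 1 then becomes zero, and the scan date no longer depends on how EOT is dated. The cost is protocol wording and a flow-chart footnote, with the 12-week interval unchanged. Some patients who stop will be scanned a few weeks earlier than under the EOT clock, and Surveillance clinic dates may need aligning.
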